Pivotal Study of Subcutaneous Tibial Nerve Stimulation with eCoin[®] for Urgency Urinary Incontinence.

- While other device modalities are more invasive (i.e., sacral neuromodulation or botulinum toxin of the bladder) and drug therapy is fraught with poor compliance, as an investigational device, the study will only include patients who have an inadequate response to second or third line therapies.
- Some subjects may not receive clinical benefit from eCoin[™] therapy, but are to continue with follow-up until study completion even if they ask for eCoin[™] to be explanted. Some individuals who initially do not receive clinical benefit may benefit from late response and cumulative effects of treatment.
- Subjects are intended to be without pharmacological medications for overactive bladder. If the addition of medications is medically necessary as described herein, such information will be collected and reported.

3-4 Study Procedures

All subjects will be followed for 48 weeks post-activation (which is the same as 52 weeks post-implantation). A 3-day voiding diary will be collected that reports the number and type of incontinence episodes, number of micturitions; and administering questionnaires including the OABq, and PGI-I at 4, 8, 12, 24, 36, and 48 weeks post-activation.

The follow-up study visits are described in relationship to the initial activation visit occurring 4 weeks after implantation of the study device. Thus, 52 weeks post-implantation occurs at the 48 weeks post-activation visit, and 28 weeks post-implantation occurs at the 24 weeks post-activation visit. See Visit Overview 3-4-2 for exact timing of such visits. For any enrolled subject who is not activated, the same schedule will be followed as if the subject were activated.

All subjects are expected to remain free of pharmacological medications for overactive bladder, unless medically necessary, until the primary endpoint is measured at 48 weeks post-activation. Subjects who are taking pharmacologic medication at screening should be washed off OAB medications for a period of 2 weeks prior to the baseline visit.

All subjects will either be explanted after the study visit at 48 weeks post-activation, or, if they consent to extended follow up, they will be explanted shortly after their 96 week post-activation visit or their 144 week post-activation visit.

COVID-19 Considerations

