Due to the COVID-19 pandemic, subjects may not be able or would be at risk coming in to the investigational site for remaining follow up visits. As an alternative, subjects may complete remote visits, in which all study activities can be performed with the exception of taking vitals. The patient will electronically transmit their diary and OABq responses to the investigational site personnel, through either pictures, scans, or fax, and review all other items over the phone. Changes in study visit schedules, remote visits, missed visits, or patient discontinuations due to COVID-19 will be documented and will be included in the final study visit report.

3-4-1 Recruitment Plans

Investigators will identify patients who are currently under their direct care, and contact patients who appear to qualify from medical records. Investigators will also seek referrals from other urology, urogynecology, gynecology, and primary care practices. A member of the site's clinical research team shall assess whether the individual seems suitable for the study. The patient should have a medical history of overactive bladder

Original Application for an Investigational Device Exemption

Pivotal Study of Subcutaneous Tibial Nerve Stimulation with eCoin[®] for Urgency Urinary Incontinence.

with urgency urinary incontinence. Patients with urgency urinary incontinence who appear to meet the inclusion/exclusion criteria from medical records will be contacted by the Investigator or designated study staff and presented with the opportunity to participate in the study, including:

- reason for being identified (OAB with urgency urinary incontinence)
- description of therapy
- potential benefits
- potential risks
- compensation (see 3-11-6)

Pivotal Study of Subcutaneous Tibial Nerve Stimulation with eCoin[®] for Urgency Urinary Incontinence.

Patients who remain interested will be brought into the research clinic for further screening and informed consent.

3-4-2 Visit Overview

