The ordered enrollment process consists of screening (including obtaining written consent), completing the baseline evaluation, implanting the eCoin[™] system, and establishing the participant's amplitude setting. This Section includes a table of the visit schedule and contents thereof. The timing of visits 1 through 4, 12 and 13, is described in relationship to the visit named, while the timing of visits 6 through 11 is described in relationship to the initial activation visit (Visit 5). A revision procedure would not reset the initial activation date.

For visits involving a 3-day diary, the diary should be completed over 3 consecutive days during the 7 days prior to each indicated visit. The site should give patients a telephone call to remind them of the diary requirement at least 3 days prior to each follow-up visit.

- Visit 1: Screening Procedures (informed consent, urinalysis, PVR, history and physical examination, subjects begin 2 week wash-off of OAB medications if applicable, concomitant medication therapy review, eligibility determination)
- Visit 2: Baseline Assessments (3-day voiding diary, OABq, subject receive TENS instructions, final eligibility determination) (Time: Between 3 and 28 days from Visit 1)
- Visit 3: Implant Procedure (Return of 3-day voiding diary completed alongside TENS, adverse event assessment, concomitant therapy review, patient surveys including OABq, patient satisfaction, and patient global impression of improvement, return of the TENS unit, pre and post-op pictures) (Time: Between 7 and 35 days from Visit 2)
- Visit 4: Incision Healing Check (week 2) (Time: Between 9 and 19 days from Visit 3) including pictures
- Visit 5: Initial Activation (week 4) (Time: Between 23 and 43 days from Visit 3) including pictures
- Visit 6 (4 weeks post-activation): Follow-up Assessments (3-day voiding diary, adverse event assessment, concomitant medication therapy review, patient surveys including OABq, patient satisfaction, and patient global impression of improvement) (Time: Between 23 and 33 days from Visit 5)
- Visit 7 (8 weeks post-activation): Follow-up Assessments (3-day voiding diary, adverse event assessment, concomitant medication therapy review, patient surveys including OABq, patient satisfaction, and patient global impression of improvement) (Time: Between 51 and 61 days from Visit 5)

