- Visit 7b (8 weeks post-activation): Second programming to make any adjustments (Time: Between 51 and 68 days from Visit 5; Visit 7b may occur on the same day as Visit 7 or about one week following Visit 7)
- Visit 8 (12 weeks post-activation): Follow-up Assessments (3-day voiding diary, adverse event assessment, concomitant medication therapy review, patient surveys including OABq, patient satisfaction, and patient global impression of improvement) (Time: Between 79 and 89 days from Visit 5)

Pivotal Study of Subcutaneous Tibial Nerve Stimulation with eCoin[®] for Urgency Urinary Incontinence.

- Visit 9 (24 weeks post-activation): Follow-up Assessments (3-day voiding diary, adverse event assessment, concomitant medication therapy review, patient surveys including OABq, patient satisfaction, and patient global impression of improvement) (Time: Between 163 and 173 days from Visit 5)
- Visit 9b (24 weeks post-activation, described elsewhere as 28 weeks post-implantation): Third programming to make any adjustments (Time: Between 163 and 180 days from Visit 5; Visit 9b can occur on the same day as Visit 9 or about one week following Visit 9)
- Visit 10 (36 weeks post-activation): Follow-up Assessments (3-day voiding diary, adverse event assessment, concomitant medication therapy review, patient surveys including OABq, patient satisfaction, and patient global impression of improvement) (Time: Between 247 and 257 days from Visit 5)
- Visit 10b (36 weeks post-activation): Fourth programming to make any adjustments (Time: Between 247 and 264 days from Visit 5; Visit 10b can occur on the same day as Visit 10 or about one week following Visit 10)
- Visit 11 (48 weeks post-activation, described elsewhere as 52 weeks post-implantation): Follow-up Assessments (3-day voiding diary, adverse event assessment, concomitant medication therapy review, patient surveys including OABq, patient satisfaction including final study questionnaire, and patient global impression of improvement) May be done remotely if necessary with consideration to COVID-19. (Time: Between 331 and 341 days from Visit 5)
- Visit 12 (For subjects who consent to extended follow up and have their device in place at 2 years) (96 weeks post-activation): Follow-up Assessments (3-day voiding diary, adverse event assessment, concomitant medication therapy review, patient surveys including OABq, patient satisfaction, and patient global impression of improvement) (Time: Between 662 and 682 days from Visit 5)

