- 3) Assessments at visits 4, 8, 12, 24, 36, and 48 weeks post-activation contain the same procedures. They are described in the Visit Overview Section 3-4-2. The 8, 24, and 36 week visits will include a scheduled reprogramming to check in on how the patient is doing with the device settings.
- 4) All other visits are also described in the Visit Overview Section 3-4-2.

At the follow-up visit 48 weeks post-activation, the primary effectiveness endpoint will have been reached.

3-4-12 Escape Procedure

Unless judged medically necessary, medications for overactive bladder are not allowed until the primary effectiveness endpoint is reached at 48 weeks post activation. Agents added or withdrawn are at the discretion of the Investigator and managing physician. Any such adjustment is to be noted on the CRFs. Patients are also asked at each follow-up visit whether they have taken any medication for overactive bladder. Any answer of “yes” will be reported on the visit CRF and a corresponding concomitant medication CRF.

3-5 Study Objectives

3-5-1 Primary and Key Secondary Objectives

3-5-1-1 Primary Effectiveness Objective

To assess the effectiveness of eCoin[™] on the proportion of subjects achieving at least a 50% improvement in the number of urgency urinary incontinence episodes per 24 hours on a 3 day voiding diary after 48 weeks of therapy.

3-5-1-2 Key Secondary Effectiveness Objective

To assess the effectiveness of eCoin[™] on the proportion of subjects achieving at least a 50% improvement in the number of urgency urinary incontinence episodes per 24 hours on a 3 day voiding diary after 24 weeks of therapy.

3-5-1-3 Primary Safety Objective

To assess safety 52 weeks after implantation of eCoin[™].

Pivotal Study of Subcutaneous Tibial Nerve Stimulation with eCoin[®] for Urgency Urinary Incontinence.

3-5-1-4 Key Secondary Safety Objective

To assess safety 28 weeks after implantation of eCoin[™].

3-5-2 Secondary Objectives

The following objectives refer to measures taken after 24 and 48 weeks of therapy.

To assess the proportion of subjects achieving 75% improvement in the number of urgency urinary incontinence episodes per 24 hours on a 3 day voiding diary.

To assess the proportion of subjects achieving 100% improvement in urgency urinary incontinence episodes (“Dryness”) per 24 hours on a 3 day voiding diary.

To assess the reduction in the number of urgency urinary incontinence episodes per 24 hours on a 3 day voiding diary.

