- 1) AEs that are device-related resulting in a revision surgery or explant (explant for reasons other than for normal end of life – e.g. battery depletion) for which the patient presents to the PI.
- 2) AEs that occur during or related to an explant procedure performed at the normal device end of life.

3-8-7 Subject Withdrawal & Termination

This section describes reasons for withdrawal of subjects and termination of the study. A Statistical Analysis Plan (SAP) will describe in detail the methods for handling data from subjects who withdraw, or are withdrawn, early from the study.

3-8-7-1 Early Withdrawal of Subjects

Subjects may voluntarily withdraw from the study for any reason at any time. They may be considered withdrawn if they state an intention to withdraw, fail to return for visits, or become lost to follow-up for any reason. The devices must be recommended to be explanted if the subject is withdrawn.

3-8-7-2 Terminating Subject Participation

A subject's continued participation in the study must be terminated if in the Investigator's opinion, continued participation would be detrimental to the subject's well-being. If the subject is unwilling or unable to attend all remaining follow-up visits, or if subject is lost to follow-up, the subject's continued participation must be terminated. If the subject is explanted for any reason, subject participation must be terminated.

The subject's eCoin[™] system must be recommended to be explanted if the subject's participation is terminated.

3-8-7-3 Withdrawal/Termination Procedures

If premature withdrawal occurs for any reason, the Investigator must make every effort to determine the primary reason for a subject's premature withdrawal from the study and record this information on the Case Report Form for reporting to the Sponsor.

Pivotal Study of Subcutaneous Tibial Nerve Stimulation with eCoin[®] for Urgency Urinary Incontinence.

Subjects enrolled in the study will not be replaced if they withdraw or are terminated from the study after device activation. Provisions for device explantation will be arranged.

3-8-7-4 Early Study Termination

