The study can be terminated at any time for any reason by Valencia Technologies. Should this be necessary, the subjects should be seen as soon as possible and treated as described in the early withdrawal section for a prematurely withdrawn subject. The Investigator may be informed of additional procedures to be followed in order to ensure that adequate consideration is given to the protection of the subjects' interests. The Investigator will be responsible for informing the IRB of the early termination of the trial. If required, provisions for the explant of the eCoin[™] system will be arranged.

3-8-7-5 Data Collection and Follow-up for Withdrawn Subjects

Subjects who are not implanted with the eCoin study device will not be followed after termination or withdrawal from the study.

3-8-8 COVID-19 Related Delayed Explantation

Subjects who do not or did not consent to extended follow up may have an explant well beyond the final study visit window because of COVID-19 considerations. However, the database may be locked through the 48 week final study visit following complete monitoring. Subjects who do not or did not consent to extended follow up will not undergo study procedures beyond those originally consented but will continue to be followed for adverse events and complaints until explantation is performed and healing is observed. This will be done under the extension portion of this protocol.

3-8-9 Data and Safety Monitoring Board

A Data and Safety Monitoring Board of at least three members will review data including a quarterly report of Adverse Events. This DSMB will meet by telephone monthly until all subjects reach one month post-implantation and at least quarterly until all subjects reach 52 weeks post-implantation to review aggregate and individual subject data related to safety, data integrity, and overall conduct of the trial. The DSMB will be responsible for reviewing adverse events. The DSMB will provide recommendations to continue or terminate the trial depending upon this review. A DSMB charter is set forth in a DSMB Charter document (see 4-10).

Pivotal Study of Subcutaneous Tibial Nerve Stimulation with eCoin[®] for Urgency Urinary Incontinence.

3-9 Data Analysis Plan

3-9-1 Data Collection

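### A subject who is merely unable to attend must be terminated, and the remote visit that could still obtain the week-48 diary is offered only for COVID-19

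*Protocol*

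**What the plan says.** **Termination.** Protocol 3-8-7-2 sets the trigger as "If the subject is unwilling or unable to attend all remaining follow-up visits, or if subject is lost to follow-up". Participation must then end, and explant of the device must be recommended.

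**Data after termination.** Protocol 3-8-7-5, the section on data collection for withdrawn subjects, is a single sentence: "Subjects who are not implanted with the eCoin study device will not be followed after termination or withdrawal from the study". It gives no procedure for implanted subjects, who make up the primary analysis population (Protocol 3-9-3-2; SAP 5.1).

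**Remote visits.** These appear in two places. The COVID-19 paragraph of Protocol 3-4 says: "As an alternative, subjects may complete remote visits, in which all study activities can be performed with the exception of taking vitals". Under Visit 11 (week 48), Protocol 3-4-2 says: "May be done remotely if necessary with consideration to COVID-19". Otherwise the subject brings the diary to the appointment (3-4-11).

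**The diary.** Protocol 3-4-2: "the diary should be completed over 3 consecutive days during the 7 days prior to each indicated visit".

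**Missing week-48 outcome** (Protocol 3-9-6; SAP 10.1):
- device known to be in place, or explanted for an MRI: multiple imputation assuming missing at random;
- device explanted for any other reason, or device status unknown: non-responder.

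**Safety.** The primary safety outcome covers device-related adverse events to 52 weeks after implantation (3-9-3-3-3). Missing safety data, apart from partial dates, stay missing (3-9-6).

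**The concern.** Someone who moves away, loses mobility or becomes a carer may be willing to complete a diary and answer questions by telephone. Followed literally, the protocol terminates that person and advises removal of the device. It then does not say that a week-48 diary, an adverse event review or the device status will be sought.

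An outcome that could have been observed is then imputed. If the subject takes the advice and is explanted before week 48, it is scored as non-response. In a single-arm implant trial of about 120 subjects, planned safety observation for that person also stops short of the 52-week endpoint.

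**Working it through.** **1. Setting the texts side by side**

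| Question | Where | Answer |
|---|---|---|
| Can the outcome be collected without a clinic visit? | 3-4-2 | Yes; the diary is kept in the week before the visit |
| Does the protocol regard remote collection as adequate? | 3-4, COVID-19 paragraph | Yes, for everything but vitals |
| Is it open to a subject unable to attend for another reason? | 3-4; 3-4-2, Visit 11 | Not provided for |
| What happens to that subject? | 3-8-7-2 | Terminated, explant recommended |
| What is collected afterwards if implanted? | 3-8-7-5 | Not stated |
| How is the missing outcome handled? | 3-9-6; SAP 10.1 | Imputed, or non-responder, according to device status |

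The gap is in data collection. The analysis rules for a missing outcome exist.

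**2. The plan's own power figures**

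Inputs (Protocol 3-9-4; SAP 6): N=120, null response 40%, one-sided 2.5%, success if the lower limit of the two-sided 95% Clopper-Pearson interval exceeds 40%. Stated power is 80%, 90% and 95% at true rates of 53%, 55% and 57%.

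- Normal approximation with continuity correction: 79.9%, 90.0% and 95.8%. This is close to the stated figures.
- Exact rule: the smallest passing count is 60 of 120 (lower limit 0.4074; 59 gives 0.3993). Power is 77.4%, 88.3% and 94.9%.

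**3. Effect for the cooperative subject with the device in place**

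Pass mark: the smallest x with BetaInv(0.025; x, n−x+1) > 0.40. Power: P(X ≥ pass mark | n, 0.55). Type I error: the same tail at 0.40. Imputation is approximated by dropping the affected subjects. This ignores what the imputation model takes from earlier diaries. The numbers affected are assumptions, because the documents give no dropout rate.

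| Enrolled | Affected | n | Pass mark | Power at 55% | Type I error |
|---|---|---|---|---|---|
| 120 | 0 | 120 | 60 | 88.3% | 1.67% |
| 120 | 1 | 119 | 59 | 90.0% | 2.14% |
| 120 | 2 | 118 | 59 | 88.2% | 1.76% |
| 120 | 3 | 117 | 58 | 89.8% | 2.25% |
| 120 | 4 | 116 | 58 | 88.0% | 1.84% |
| 135 | 0 | 135 | 66 | 93.5% | 2.24% |
| 135 | 2 | 133 | 65 | 93.4% | 2.35% |
| 135 | 4 | 131 | 64 | 93.3% | 2.46% |

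The pass mark moves in whole subjects, so power rises and falls by more than the loss itself. Comparing like with like (0, 2 and 4 affected), four affected subjects cost 88.3 − 88.0 = 0.3 points at N=120 and 93.5 − 93.3 = 0.2 points at N=135. Type I error stays below 2.5% throughout.

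**4. Direction**

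Scoring an explanted subject as a non-responder can only lower the observed rate. Imputation adds no bias if the missing-at-random assumption holds. Neither rule in itself favours the device.

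**The case against.** The strongest reply is that almost nothing turns on this. Power barely moves, 3-9-6 expects nearly all implanted subjects to have data, and the imputation model uses baseline and all follow-up diaries. **This stands**, and it is why the point is minor.

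A second reply is that the protocol does not forbid remote collection. By excluding only non-implanted subjects, 3-8-7-5 may imply that implanted ones are followed. That inference is fair, but no visit, diary or method is named, and 3-8-7-2 has by then ended participation. If follow-up was intended, the fix writes it down.

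A third is that safety is not wholly uncovered. Adverse events are sought at each contact, and subjects are asked to report urologic events between visits (3-8-6-4). After the study period, 3-8-6-6 asks for reports of device-related events leading to revision or explant, and of events around an end-of-life explant. This stands in part: the scheduled review to 52 weeks is still not provided for once participation ends.

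Two stronger readings are tempting.
- **A material loss of power.** One subject scored as a non-responder takes exact power at 55% from 88.3% to 86.3%. But that score requires an explant other than for MRI, or unknown device status. It does not describe a cooperative subject who is in contact and still implanted, so it is no measure of this gap.
- **A contradiction about follow-up after explant.** Protocol 3-3-3 says subjects without benefit "are to continue with follow-up until study completion even if they ask for" explant, while 3-8-7-2 ends participation on any explant. That is a separate question about a different group and does not support this point.

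The case report forms and the COVID-19 addendum to the SAP were not available. The SAP supplied is dated August 2019, so its silence on remote visits shows little.

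**Conclusion.** The point holds as a minor one. A mandatory termination rule covers subjects who are only unable to attend, and the procedure that could keep their outcome observed is restricted to COVID-19. For a cooperative subject who keeps the device, the cost is an imputed primary outcome in place of an observed one and no scheduled adverse event review to 52 weeks. For one who accepts the explant before week 48, it is a non-response.

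The power effect for the subjects directly served is about 0.3 points or less with up to four affected, assuming a true response of 55% and imputation approximated by exclusion. How many would be affected cannot be determined from the documents. The documents do not support a reading that the trial could succeed wrongly because of this rule, or that its power is materially at risk. The gain is observed data, known device status and more complete safety follow-up.

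**What to change.** 1. **Protocol 3-8-7-2.** State that inability to attend in person does not by itself end participation when the subject has not withdrawn consent and agrees to remote follow-up. Keep termination for withdrawal of consent, loss to follow-up and the investigator's safety judgement. This sentence has to change, because termination is also what triggers the explant recommendation. Whether explant is advisable for someone who cannot be seen in clinic remains a clinical decision.
2. **Protocol 3-4 and Visit 11 in 3-4-2.** Open the remote procedure to such subjects whatever the reason.
3. **Protocol 3-8-7-5.** State that implanted subjects who stop attending but have not withdrawn consent are asked remotely for the week-24 and week-48 diaries, questionnaires, adverse event review and device status.

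No analysis change is needed. A week-48 diary obtained this way with the device in place already counts as available data under Protocol 3-9-6 and SAP 10.1.

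The cost is a few sentences and a little site work. Remote visits collect no vitals. Reprogramming is also lost where those visits are missed: "The 8, 24, and 36 week visits will include a scheduled reprogramming", and stimulation is adjusted only in the clinic (3-7-4-2). If week 48 is the only visit left, vitals are the only loss.

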8. Was the patient hospitalized? If yes, provide dates.
9. Will the patient continue with treatment, and will any be missed?
10. Did the patient add or change any other associated medication and what were the changes/additions?
11. Was any other action taken?

When an AE has been recorded, the PI or sub-PI for the study must sign and approve the assessment on the Sponsor-provided form. The Study monitor will keep track of all reported AEs. A sample of the AE report form is in Attachment 4-9.

3-8-6-5 Reporting Procedures

For Serious Adverse Events (SAEs) or suspected Unanticipated Adverse Device Effects (UADEs), the Study Coordinator, the PI, and the Sponsor will be alerted. The timeline for medical review and assessment is 24 hours for SAEs and 7 days from subject reporting of non-serious unexpected device related AEs. For suspected UADEs, the Sponsor will promptly provide an expectedness determination. The Investigator must

Pivotal Study of Subcutaneous Tibial Nerve Stimulation with eCoin[®] for Urgency Urinary Incontinence.

promptly inform the Ethics Board or IRB of SAEs or determined UADEs per local reporting requirements.

The SAE form provided by the Sponsor should be completed and signed by the Investigator or physician sub-investigator and faxed or emailed to the Sponsor per the instructions on the form. The entire SAE form needs to be completed, if possible, to make available in a timely manner complete relevant information thus limiting requests for additional information. Each SAE reported on an SAE form must also be reported in the adverse event section of the CRF.

These events will be reported by the Sponsor as appropriate to the regulatory authorities according to relevant jurisdictional medical device regulations. The Investigator will receive notification of these events across all study centers from the Sponsor.

3-8-6-6 Adverse Event Reporting Period

Adverse event information will be collected throughout the entire study between Informed Consent and final follow-up. If the patient presents to the Investigator after the study period and a device-related AE is suspected, the AE should be reported to the Sponsor using the post-study AE form provided by the Sponsor. Post-study adverse events should be reported to the Sponsor after the study period if they are:

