The primary effectiveness outcome is achieving at least a 50% reduction from baseline in the number of urgency urinary incontinence episodes per 24 hours on a 3 day voiding diary after 48 weeks of eCoin[™] tibial nerve stimulation.

The proportion of responders along with its 2-sided 95% exact Clopper-Pearson confidence interval will be summarized after 48 weeks of therapy.

3-9-3-3-2 Key Secondary Effectiveness Outcome

The key secondary effectiveness outcome is achieving at least a 50% reduction from baseline in the number of urgency urinary incontinence episodes per 24 hours on a 3 day voiding diary after 24 weeks of eCoin[™] tibial nerve stimulation.

Pivotal Study of Subcutaneous Tibial Nerve Stimulation with eCoin[®] for Urgency Urinary Incontinence.

The proportion of subjects with at least 50% reduction from baseline along with its 2-sided 95% exact Clopper-Pearson confidence interval will be summarized after 24 weeks of therapy.

3-9-3-3-3 Primary Safety Outcome

The primary safety outcome is device-related adverse events from implantation to 52 weeks after implantation of eCoin[™].

All device-related adverse events up to 52 weeks after implantation of eCoin[™] will be summarized by preferred term. Tabulations of these data will include the number of subjects exposed and the number of subjects with at least one device-related adverse event.

3-9-3-3-4 Key Secondary Safety Outcome

The key secondary safety outcome is device-related adverse events 28 weeks after implantation of eCoin[™].

All device-related adverse events up to 28 weeks after implantation of eCoin[™] will be summarized by preferred term. Tabulations of these data will include the number of subjects exposed and the number of subjects with at least one device-related adverse event.

3-9-3-3-5 Secondary Outcomes

The secondary outcomes listed in this section are based on data after 24 and 48 weeks from activation (28 and 52 weeks after implantation). These outcomes, which are for descriptive purposes, will not be formally analyzed statistically. The SAP will describe in detail analyses of the secondary outcomes.

- Achieving 75% improvement in the number of urgency urinary incontinence episodes per 24 hours on a 3 day voiding diary.
- Achieving 100% improvement in urgency urinary incontinence episodes (“Dryness”) per 24 hours on a 3 day voiding diary.
- Reduction from baseline in the number of urgency urinary incontinence episodes per 24 hours on a 3 day voiding diary.

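### Protocol 3-8-7-2 ends participation at explant, so active adverse event follow-up can stop well short of the 52-week primary safety endpoint

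*Protocol*

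**What the plan says.** Protocol 3-8-7-2 (Terminating Subject Participation) is unconditional: "If the subject is explanted for any reason, subject participation must be terminated". It has no exception for safety follow-up.

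Other sections point elsewhere or leave the matter open:

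- Protocol 3-4 has all subjects followed to 48 weeks post-activation, that is, 52 weeks post-implantation. It adds: "For any enrolled subject who is not activated, the same schedule will be followed as if the subject were activated".
- Protocol 3-8-7-5 restricts follow-up only for the never-implanted: "Subjects who are not implanted with the eCoin study device will not be followed after termination or withdrawal from the study". For a subject who was implanted and then explanted it gives neither a rule nor a schedule.
- Protocol 3-3-3 says that subjects without benefit "are to continue with follow-up until study completion even if they ask for" the device to be removed.

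On safety, Protocol 3-9-3-3-3 states: "The primary safety outcome is device-related adverse events from implantation to 52 weeks after implantation". SAP 11.1 counts AEs by subject in the ITT population, meaning everyone who underwent the implant procedure. Protocol 3-9-6 leaves missing safety data as missing, apart from partial dates. SAP 11.2 gives all subjects a healing check two weeks after explantation.

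Protocol 3-8-6-6 covers reporting after the study period. It applies "If the patient presents to the Investigator after the study period and a device-related AE is suspected", and then lists two reportable types: "AEs that are device-related resulting in a revision surgery or explant" and "AEs that occur during or related to an explant procedure performed at the normal device end of life".

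**The concern.** Sites are given two instructions for the same subject, and only 3-8-7-2 addresses explant directly and in mandatory terms. A site that follows it stops scheduled AE questioning long before week 52. The subject stays in the denominator of every AE table, so the unobserved weeks are treated as event-free.

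The loss is not random. Early explants tend to follow a wound, pain or infection problem, or lack of benefit. A subject explanted for a device-related AE is already counted once; what can be missed is a later, different event and the date of resolution. For a subject explanted for another reason, a first device-related event after the healing check can be missed altogether. Both losses make the device look safer. Late problems are plausible: 3-7-4-3 lists wound complications persisting beyond 8 weeks, and 2-2-2-3 reports an infection at six months that led to explant.

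**Working it through.** The plan gives no figure for post-explant loss, so its size has to be built from the prior studies.

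**Explant rates**

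- Hypertension study (2-2-2-3, 3-7-4-3): two explants in 48 subjects, 2/48 = 4.2%, which reproduces the protocol's figure. The exact 95% interval is 0.5% to 14.3%. This is a rough analogue: median nerve, and 96 devices in 48 subjects.
- OAB feasibility study (3-7-4-3): one explant is described among 46 subjects, 1/46 = 2.2% (0.1% to 11.5%). No total is given, so this is a minimum.

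**Expected early explants at the target of 120**

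- 120 × 1/46 = 2.6, about 3.
- 120 × 0.042 = 5.0, about 5.
- At the maximum of 135 the corresponding numbers are about 3.0 and 5.7.

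**Weeks unobserved per explanted subject** = 52 − (explant week + 2), where the 2 is the healing check.

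- Explant at week 4, assumed for a removal before activation as in the OAB study: 52 − 6 = 46 weeks (88%).
- Explant at week 26, as for the six-month infection: 52 − 28 = 24 weeks (46%).

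**Share of planned person-weeks**, with 120 × 52 = 6,240 as the denominator:

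| Explants | At week 26 | At week 4 |
|---|---|---|
| 3 | 3 × 24 = 72 (1.2%) | 3 × 46 = 138 (2.2%) |
| 5 | 5 × 24 = 120 (1.9%) | 5 × 46 = 230 (3.7%) |

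As a cross-check, spread the explants evenly over the year and ignore the healing check. About 26 weeks are then lost per explant. That is about 69 person-weeks (1.1%) at 2.2% and 131 (2.1%) at 4.2%, the same order.

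**Effect on an AE rate.** Each subject whose event is missed lowers a preferred-term rate by 1/120 = 0.83 percentage points.

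**Contacts needed to close the gap.** A subject explanted before activation has six scheduled visits left (weeks 4, 8, 12, 24, 36 and 48). One explanted 26 weeks after implantation is at about week 22 post-activation and has three left (weeks 24, 36 and 48). For 3 to 5 explants that is 3 × 3 = 9 to 5 × 6 = 30 contacts.

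**The case against.** The strongest reply is that the protocol does not settle on ending follow-up. Because 3-8-7-5 bars only the never-implanted, it implies that implanted subjects can be followed after termination. That stands, and it makes this an unresolved conflict and not a certain loss. But an implication without a schedule will not produce consistent data across about 20 centers.

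Several stronger readings are tempting and should not be drawn:

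- **That 3-3-3 flatly contradicts 3-8-7-2.** Its next sentence says that some subjects may respond late through cumulative treatment, which makes sense only if the device stays in. Read whole, it more naturally discourages explant for lack of benefit.
- **That events after an early explant are unreportable.** The two listed types do not fit such events well, but the general sentence in 3-8-6-6 reaches any suspected device-related AE if the patient presents. The weakness is that reporting becomes passive.
- **That a serious event rate could be hidden entirely**, for example a reported 0 of 120 standing for 5 of 120. This would need every explanted subject to have the same new event after the healing check and nobody else to have it. Protocol 3-6 also expects serious infections within one month of implantation.
- **That the secondary effectiveness results are materially biased.** SAP 10.3 does not impute the changes from baseline, PGI-I or satisfaction, so explanted subjects do leave those summaries. Protocol 3-9-3-3-5 makes them descriptive, however, and the 75% and 100% responder outcomes are imputed like the primary.

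The plan also offers some transparency. SAP 8.1 lists early terminations with study day and reason, SAP 8.4 summarises duration of implantation, and SAP 11.1 lists AE resolution and outcome. A reader could see that follow-up was cut short, but not what happened afterwards.

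**Conclusion.** The point holds as a conflict over conduct and follow-up. If 3-8-7-2 is followed, active AE ascertainment for an explanted subject ends after 6 to 28 of the 52 weeks in the two cases worked. The expected extent is about 3 to 5 of 120 subjects and about 1% to 4% of person-weeks. This rests on explant rates of 2.2% to 4.2%, both from small studies with wide intervals, and on explants at week 4 or week 26.

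A reader might infer that the primary effectiveness result is at risk. The documents do not support that: Protocol 3-9-6 and SAP 10.1 score a non-MRI explant before week 48 as a non-responder, and MRI explants are multiply imputed.

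The case for change is not the size of the loss. It is that the loss falls on informative subjects, in the primary safety outcome, and can be largely avoided at little cost.

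**What to change.** - **Protocol 3-8-7-2:** state that explant ends therapy, not safety follow-up. Unless consent is withdrawn, AE checks continue on the existing schedule to 52 weeks after implantation, by remote visit or telephone if needed. Protocol 3-4 already allows remote visits because of COVID-19. Ongoing device- or procedure-related AEs are followed to resolution.
- **Protocol 3-8-7-5 and 3-8-6-6:** align both. Say that implanted subjects are followed after explant, and name device- or explant-related events after an early explant as reportable.
- **If week-48 diaries are also collected after explant:** add to Protocol 3-9-6 and SAP 10.1 that a non-MRI explant before week 48 is a non-responder whether or not a diary exists. The present rule is framed as missing-data handling, and a post-explant diary would otherwise leave room for argument. Report such diary data only as a supplementary summary. Moving them into the main SAP 10.3 summaries would change the question being estimated, and they may reflect OAB medication or other treatment.

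The cost is a few sentences and about 3 to 6 already scheduled or remote contacts per explanted subject, 9 to 30 in all for 3 to 5 explants. Some subjects will decline, so the loss is reduced and not removed.
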